2.8.4 Other safety data

2.8.4.1 ECG

The (uncorrected) QT interval will be corrected according to Fridericia's formulae. The incidence rates of newly occurring or worsening clinically notable ECG abnormalities will be summarized. The same approach as for notable laboratory values will be used to define a newly occurring notable QTc value and a worsening notable QTc value. Notable ECG values will be listed.

Notable criteria are:

- QTcF > 500 msec or
- increase from baseline > 60 msec

If the single ECG shows a QTcF > 500 ms (males or females), 2 additional ECG replicates should be recorded to confirm the safety findings and copies forwarded to the central ECG laboratory for assessment. The results from those triplicate ECGs will be averaged and analysed as one value for summary and notable tables.

2.8.4.2 Vital signs

The number and percentage of subjects with clinically notable vital signs will be presented. Notable vital sign values will be listed.

Notable criteria are:

Variable	Criterion value		Change relative to baseline
Heart rate/pulse	120 bpm 50 bpm	and an and a	increase of ≥ 15 bpm decrease of ≥ 15 bpm
Systolic blood pressure	180 mm Hg 90 mm Hg	and an and a	increase of ≥ 20 mm Hg decrease of ≥ 20 mm Hg
Diastolic blood pressure	105 mm Hg 50 mm Hg	and an and a	increase of ≥ 15 mm Hg decrease of ≥ 15 mm Hg
Weight	Baseline weight (kg)	and an and a	increase of ≥ 7% decrease of ≥ 7%

bpm= beats per minute

Data of subjects with newly occurring notable vital signs abnormalities will be listed in an additional listing.

2.8.4.3 Physical examination

Physical examination including examination of skin will be source documentation only.

2.9 Pharmacokinetic endpoints

Scatter plots of EMA401 plasma concentrations will be displayed in linear and semilogarithmic view in a CSR addendum or in a separate report.

2.10 PD and PK/PD analyses

Evaluation of effect of EMA401 exposure on efficacy variables (e.g. change from baseline of pain score), via the development of a continuous descriptive Pharmacokinetics/ Pharmacodynamics (PK/PD) was planned in the protocol. All population PK/PD analyses and simulations were to be carried out using a non-linear mixed-effects modelling approach. Due to early study termination the planned model based exposure-response analysis will not be performed and replaced with a graphical assessment of the exposure-response relationship.

[figure not shown]
This will be reported in a separate report.

2.11 Patient-reported outcomes

Please refer to efficacy analysis for details on all Patient Reported Outcomes (PRO).

2.12 Biomarkers

Not applicable.

2.14 Interim analysis - Safety

The DMC will review cumulative safety data, including patient narratives for deaths, serious adverse events (SAEs), discontinuations due to adverse events and cases of interest (allergic dermatitis, and clinically significant abnormal hepatic and hematology values).

The details of the analysis required for DMC will be specified in a separate DMC analysis plan and not repeated here in detail.

3 Sample size calculation

The calculation of power for the testing procedure mentioned in Figure 2-1 is based on the following assumptions:

- The treatment difference of 100 mg b.i.d. vs. placebo was assumed as 0.7, 0.8 and 0.9 points, for the primary efficacy variable (weekly mean of the 24-hour average pain score). A treatment difference of 0.7 points was observed for the 100 mg b.i.d. dose vs. placebo for weekly mean of the 24-hour average pain score (NRS) in the Study EMA401-003 during a 4-week treatment period. The standard deviation is 2.6 points (based on data from pregabalin historical trials - see [FDA Approval Package Medical Review, 2004](#)) is assumed for the primary efficacy variable. In Study EMA401-003 in PHN patients, a standard deviation of approximately 2.0 points was observed. A slightly higher value of 2.6 has been chosen to account for a possible higher variability due to a higher number of centers and due to multiple imputations (as opposed to single imputation) in the analysis. It is also assumed that the same standard deviation holds for the PDN population.
- Treatment differences of 5 points for Pregabalin and 10 points for Duloxetine on NPSI total score were observed via an indirect comparison using the results from Tesfaye (2013) which is an active control study (Pregabalin vs Duloxetine) and Kalliomäki (2013) which is a placebo controlled study (AZD2423 vs placebo). The standard deviation was derived as 16 points using the results from Kalliomäki (2013). A correlation of approximately 0.2 was observed between the baseline scores of NRS and NPSI total score in Freeman et al (2014). The power of the study was calculated assuming correlation coefficient values of 0 and 0.2. Since the power values obtained for correlation values of 0.2 and 0 are similar, in a conservative scenario the results reported herein are for correlation value of 0.

Since the NPSI has not been studied in the EMA401-003 study, to mitigate the risk of uncertainty on the value of treatment difference and standard deviation, the effect size (treatment difference/ standard deviation) of NPSI total score has been considered for the calculation of power. The power of the study was calculated for different effect sizes ranging in 0.1, 0.5 for NPSI total score corresponding to 100 mg.

Under the assumptions of a 0.8 point treatment difference between 100 mg b.i.d. and placebo, a standard deviation as 2.6 for the primary efficacy variable and an effect size of 0.4 for 100

[figure not shown]
mg b.i.d. for the key secondary variable, N=200 patients per treatment arm will provide approximately 85% power to show that 100 mg b.i.d. is statistically significant over placebo for the primary efficacy variable, using the testing procedure mentioned in Figure 2-1. The power of showing the statistical significance of 100 mg b.i.d. dose in terms of the key secondary variable will be 84% under the same scenario. If we assume the treatment difference of 0.7 for the NRS as observed in the 4-week PoC study and the effect size for NPSI as 0.35, then the power for the primary objective will be 77% and that for the key secondary objective will be 72%. If the treatment difference between 100 mg b.i.d. and placebo is 0.9 for the NRS, and effect size is 0.45 for 100 mg b.i.d. for the NPSI, the power increases to 94% for the primary objective. The corresponding power for the key secondary objective increases to 93%.

4 Change to protocol specified analyses

An additional population, the mFAS population, has been defined.

The following analyses were specified in the protocol but will not be performed due the early termination of study:

- first and third supplementary analysis to the primary analysis
- tipping point analysis
- supplementary responder analyses
- ANCOVA analyses for BPI-SF, worst NRS pain score, ISI, [REDACTED]
- proportional odds model for PGIC
- analyses regarding maintenance effect of EMA401 over placebo
- time to "sustained" pain reduction
- Apart from analyses of clinical abnormalities summaries of laboratory data, vital signs and ECG intervals have been removed
- Shift tables of laboratory data
- No safety figures will be presented
- Bazett correction for QTc

The following analyses have been added:

- sensitivity analyses on modified full analysis population
- analyses of TEAEs with onset before study termination date

The analyses of patient disposition for the treatment and treatment withdrawal epoch will be based on the FAS population only

Analyses of duration of exposure to study treatment will be based on the SAF population only.

Due to the early study termination only a few patients has been included in the region 'America'. To avoid convergence problems the covariate region has been removed from the ANCOVA model and from the logistic regression.

5 Appendix

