List of abbreviations

ACR	Albumin-Creatinine Ratio
AE	Adverse Event
ALP	Alkaline Phosphate
ALT	Alanine Aminotransferase
ANCOVA	Analysis of covariance
AST	Aspartate Aminotransferase
ATC	Anatomic Therapeutic Chemical classification
b.i.d.	twice a day
BPI-SF	Brief Pain Inventory-Short Form
CRO	Contract Research Organization
CSR	Clinical Study Report
DAR	Dose Administration Record
DMC	Data Monitoring Committee
DN4	Douleur Neuropathique en 4 Questions
ECG	Electrocardiogram
eCRF	Electronic Case Report Form
e-diary	Electronic diary
EU	European Union
FAS	Full Analysis Set
FDA	Food and Drug Administration
GGT	gamma-glutamyltransferase
HIV	Human Immunodeficiency Virus
INR	International Normalized Ratio
IRT	Interactive Response Technology
ISI	Insomnia Severity Index
J2R	Jump to reference
LFT	Liver function test
LoE	Lack of efficacy
MAR	Missing at random
mFAS	Modified Full Analysis Set
MedDRA	Medical dictionary for regulatory activities
NPSI	Neuropathic Pain Symptom Inventory
NRS	Numeric Rating Scale
NSAID	Nonsteroidal Anti-inflammatory Drugs
PCR	Protein-Creatinine Ratio
PDN	Painful Diabetic Neuropathy

PHN	Post-Herpetic Neuralgia
PK	Pharmacokinetics
PGIC	Patient Global Impression of Change
PRO	Patient Reported Outcome
█	█
QTc	Corrected QT interval
QTcB	Bazett QT correction formula
QTcF	Fridericia QT correction formula
SAE	Serious Adverse Event
RDO	Retrieved drop-out
SAF	Safety population
█	█
SSRI	Selective Serotonin Reuptake Inhibitor
TBL	Total bilirubin
TD	Study Treatment Discontinuation
TEAE	Treatment-Emergent Adverse Events
ULN	Upper limit of Normal
USM	Urgent Safety Measures
VRS	Verbal Rating Scale
WHO	World Health Organization

Amendment 1

This amendment of the statistical analysis plan (SAP) is largely based on changes induced due to the early termination of the CEMA401A2202 study. 137 patients out of 400 planned patients have been randomized. As the number of patients included in the study is considerably reduced, an abbreviated Clinical Study Report (CSR) that still meets all requirements for reporting and disclosure of the demographics, primary endpoint, secondary endpoints and safety results to public registries will be created.

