The primary analysis on the change from baseline to Week 12 in the weekly mean of the 24-hour average pain score will be performed as originally planned. Besides the primary estimand, which is of main clinical interest, the supplementary estimand, which provides insight into the magnitude of improvement in efficacy that might be achieved if all patients were able to take EMA401 as prescribed for 12 weeks, will be analysed. The other planned supplementary estimands will be dropped, as they are of minor interest in the situation with many study treatment discontinuations due to trial termination in the scope of the Urgent Safety Measures (USM).

To support the primary analysis and to get an idea about the effect that might be achieved if the trial had not been terminated and if all patients had the chance to complete the Week 12 assessment, a sensitivity analysis on a modified population will be performed. The modified full analysis set will include all patients who had a chance to complete the study before the termination date, i.e. who had been randomized at least 12 weeks before study termination date.

Similar considerations were made for the key-secondary endpoint.

Due to the considerably reduced number of patients who completed the study, only descriptive subgroup analyses will be provided. Moreover, the secondary endpoints will also be summarized descriptively only.

1 Introduction

This statistical analysis plan (SAP) describes all planned analyses for the Clinical Study Report (CSR) of study CEMA401A2202, a Phase 2, double-blind, placebo-controlled, randomized trial to determine the safety and efficacy of EMA401 in reducing 24-hour average pain intensity score in patients with painful diabetic neuropathy.

The content of this SAP is based on the final version of protocol CEMA401A2202 (release date 15-Sep-2017). All decisions regarding final analysis, as defined in the SAP document, have been made prior to database lock and unblinding of the study data.

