1.1 Study design

The study is interventional, randomized, parallel, placebo-controlled, double-blind treatment.

The study will consist of a Screening epoch (up to 4 weeks), a double-blind Treatment epoch (12 weeks), and a double-blind Treatment withdrawal epoch (1 week).

- Patients will be randomized in a 1:1 ratio to treatment with placebo or EMA401 100 mg b.i.d.

Overall approximately 400 patients will be enrolled in the study (i.e. approximately 200 patients will be enrolled in each treatment arm).

At Week 12 (Visit 199), all patients who completed the 12-week double-blind Treatment epoch will enter the 1-week double-blind Treatment withdrawal epoch. The IRT system will indicate the unique medication number for the package of study drug to be dispensed to the patient during the double-blind Treatment withdrawal epoch. This medication number will correspond to the blinded withdrawal regimen assigned at Baseline.

Randomization will be stratified by region (America, Europe and Australia) and use of concomitant pain medication for PDN (yes/no) in order to achieve balance of treatment allocation within the stratification factors.

[figure not shown]
Primary objective of this study is to compare the efficacy of EMA401 vs. placebo in 24-hour average pain intensity score at Week 12, using an 11 point Numeric Rating Scale (NRS) by testing the superiority of EMA401 100 mg b.i.d. vs. placebo.

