2.2 Analysis sets

The following analysis populations will be used for analysis.

[figure not shown]
- The Enrolled population will include all patients who were enrolled into the study.
- The Full Analysis Set (FAS) comprises all patients to whom the study treatment has been assigned. Following the intention-to-treat principle, patients will be analyzed according to the treatment assigned to at randomization. Mis-randomized patients will be excluded from the FAS.
- The modified Full Analysis Set (mFAS) will include all patients who could have completed Week 12 by the study termination date. That means, all patients which were randomized at least 12 weeks prior to 25-Feb-2019 will be included.
- The Safety population (SAF) will include all patients who took at least one dose of study medication. Patients will be analyzed according to treatment received.

The primary efficacy analysis will be performed on the FAS.

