These patients must continue to adhere to protocol requirements (see respective protocol Table 6-2). The design feature of retrieved drop-outs, considered in order to minimize the occurrence of missing data on primary pain parameter, is exploited for the statistical analysis as follows:

- **Permanent discontinuation of study treatment due to AE, lack of efficacy (LoE) and use of prohibited medication:** If retrieved drop-out data are available, these will be used for analysis. If no data was retrieved after study treatment discontinuation, missing data will be multiply imputed based on placebo arm data, i.e. “jump to reference” (J2R) assumption for the EMA401 arm, missing at random assumption for placebo arm (Carpenter, Roger, and Kenward 2013). Of note, alternatively one could build the imputation model based on the RDO data, however, we expect sparse RDO data which will likely hinder us to build an imputation model. More details on the imputation model are specified in Section 5.
- **Permanent discontinuation of study treatment due to other reasons than AE, LoE and use of prohibited medication (including discontinuation due to USM):** If efficacy data collected after study treatment discontinuation are available (retrieved drop-out), then the retrieved drop-out data will be excluded and missing data after study treatment discontinuation will be imputed via multiple imputation method using the MAR assumption.

The multiple imputations will be carried out on the weekly mean pain score. Details on multiple imputation can be found in Section 5 of this document.

The primary objective will be achieved if the EMA401 100 mg b.i.d. dose is statistically significant versus placebo in terms of the primary efficacy variable after multiplicity adjustment. To preserve the family-wise error rate at 2.5% level when comparing the EMA401 100 mg b.i.d. dose versus placebo on the primary and key secondary endpoints (see Section 2.6), statistical testing will be carried out using the following sequentially rejective, weighted Bonferroni-type test using the graphical approach (Bretz et al 2009) mentioned in Figure 2-1.

Figure 2-1 Sequentially rejective, weighted Bonferroni type test using the graphical approach

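### SAP Amendment 1 keeps the NRS-then-NPSI test for 137 randomised patients, but Sections 1.1 and 3 still present about 400 patients and the 200-per-arm powers without marking them as the design that was not reached

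*SAP*

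**What the plan says.** The Amendment 1 page of the SAP explains that the study was terminated early and that "137 patients out of 400 planned patients have been randomized". It adds that the primary analysis of change to Week 12 "in the weekly mean of the 24-hour average pain score will be performed as originally planned".

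Section 2.5.2 keeps the success rule: "The primary objective will be achieved if the EMA401 100 mg b.i.d. dose is statistically significant versus placebo" on the primary variable after multiplicity adjustment. NRS is tested at one-sided 0.025, and NPSI is tested at the same level only if NRS succeeds. Section 2.6.2 repeats this for NPSI.

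Section 1.1 still reads: "Overall approximately 400 patients will be enrolled in the study", about 200 per arm. Section 3 says that "N=200 patients per treatment arm will provide approximately 85% power to show that 100 mg b.i.d. is statistically significant over placebo" at 0.8 points and SD 2.6. It gives primary powers of 77/85/94% at 0.7/0.8/0.9 points and key secondary powers of 72/84/93% at NPSI effect sizes 0.35/0.40/0.45. All are for 200 per arm.

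Section 4 lists the analyses dropped or added because of the termination. It does not mention sample size or power.

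**The concern.** Within one current document, the opening page gives 137 patients while the design and sample-size sections give 400 in the future tense. These are all live statements, so this is not a comparison with superseded text.

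Section 1.1 is among the sections that the document history lists as revised in this amendment, but its patient number was left alone. Elsewhere the SAP does mark abandoned plans: Section 2.10 says that the exposure-response modelling had been planned and was replaced because of the termination. Section 3 carries no such marker.

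The two formal tests will therefore be applied to about a third of the planned sample (137/400 = 34%), while the only power on record is for the full sample. A reader who takes Section 3 as describing the analysed trial would credit it with about twice the power it has at 0.8 points, and would weigh a non-significant result accordingly.

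**Working it through.** **Inputs**
- One-sided alpha 0.025, NPSI tested only after NRS: SAP 2.5.2.
- NRS differences 0.7/0.8/0.9, planning SD 2.6: SAP 3.
- NPSI effect sizes 0.35/0.40/0.45, correlation 0 for the reported powers: SAP 3.
- SD of about 2.0 observed in the 4-week PHN study EMA401-003: SAP 3. The SAP did not adopt it, so it serves here only as a sensitivity value.
- 137 randomised: Amendment 1 page. Allocation 1:1: SAP 1.1. The actual split is not given, so 68/69 is assumed.
- Complete Week 12 data and no covariate gain beyond the stated SD: assumed.

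**Formulas**
- SE = SD × √(1/n1 + 1/n2).
- Primary power = P(T > t at 0.975), where T is noncentral t with n1 + n2 − 2 df and noncentrality difference/SE.
- Key secondary power at correlation 0 = primary power × NPSI power alone.
- 95% CI half-width = t at 0.975 × SE.

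**Step 1: reproduce the plan at 200 per arm.** SE = 2.6 × √(2/200) = 0.26. Noncentralities are 0.7/0.26 = 2.69, 0.8/0.26 = 3.08 and 0.9/0.26 = 3.46. For NPSI they are 0.35/0.1 = 3.5, 4.0 and 4.5.

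| NRS difference / NPSI effect size | Primary, computed (stated) | NPSI alone | Key secondary, computed (stated) |
|---|---|---|---|
| 0.7 / 0.35 | 76.6% (77%) | 93.7% | 71.8% (72%) |
| 0.8 / 0.40 | 86.6% (85%) | 97.9% | 84.8% (84%) |
| 0.9 / 0.45 | 93.2% (94%) | 99.4% | 92.7% (93%) |

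All six agree with Section 3 within 2 points.

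**Step 2: the same calculation at 68/69, SD 2.6.** √(1/68 + 1/69) = 0.1709, so SE = 2.6 × 0.1709 = 0.444. Noncentralities are 1.58, 1.80 and 2.03 for NRS, and 2.05, 2.34 and 2.63 for NPSI.

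| NRS difference / NPSI effect size | Primary | NPSI alone | Key secondary |
|---|---|---|---|
| 0.7 / 0.35 | 34.6% | 52.9% | 18.3% |
| 0.8 / 0.40 | 43.2% | 64.2% | 27.7% |
| 0.9 / 0.45 | 52.0% | 74.4% | 38.7% |

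The half-width is 1.978 × 0.444 = 0.88 points, against 1.966 × 0.26 = 0.51 at 200 per arm. An observed difference of about 0.88 is thus needed for significance, which is more than the 0.8 assumed in the main scenario.

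**Step 3: sensitivity**
- SD 2.0: SE = 2.0 × 0.1709 = 0.342. Primary power is 52.9/64.2/74.4% and the half-width is 1.978 × 0.342 = 0.68.
- Split 60/77, SD 2.6, 0.8 points: 42.6%. The assumed split hardly matters.
- Less information: if the data are worth 120, 100 or 80 complete patients (assumed, because no Week 12 count is given), power at 0.8 and SD 2.6 is 38.7, 33.1 or 27.4%.
- Covariate gain: if 2.6 is an unadjusted SD and the covariates explain 25% of the variance (assumed), the SD becomes 2.6 × √0.75 = 2.25 and power at 0.8 is about 54%.

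**The case against.** The strongest reply is that the shortfall is disclosed before Section 1 begins. That page calls 400 the planned number, and Section 3 is a correct record of how the trial was sized. Enrolment is over, so no sample-size decision depends on new figures.

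The amendment also responds to the reduced numbers. It makes subgroup and most other secondary analyses descriptive, removes several supplementary analyses, and adds a sensitivity analysis in patients who could have reached Week 12 before termination. Section 2.5.2 plans a standardised effect size to help interpret the estimate.

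Most of this stands, and it limits what may be inferred:
- A reader might infer that Section 3 is miscalculated or that the shortfall is hidden. Neither is so.
- A reader might infer that the plan treats non-significance as proof of no effect. No section says that. Section 2.5.2 only defines when the objective is met, so an added rule on reading non-significance would be a matter of preference.
- A reader might take the 137-patient powers as upper limits, since many patients stopped treatment on termination, their later data are imputed under MAR, and "Mis-randomized patients will be excluded from the FAS". The documents do not support a one-sided claim. The SD of 2.6 was chosen partly to allow for multiple imputation. They also do not say whether it is before or after adjustment for baseline and age, so covariates may raise power.

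The reply does not remove the contradiction. Disclosing 137 on one page does not tell the reader that the powers in Section 3 no longer apply, and the SAP gives nothing in their place.

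**Conclusion.** The point holds as an internal inconsistency with a material number attached. Sections 1.1 and 3 state a sample size and powers that the analysed trial does not have, while the confirmatory rule that those powers describe is kept. At the planning SD of 2.6, primary power at 0.8 points is about 43% rather than 85%, and key secondary power about 28% rather than 84%. At SD 2.0, the value from the PHN study, primary power at 0.8 points is about 64%.

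These figures rest on the 68/69 split, complete Week 12 data and no covariate gain beyond the stated SD. They are neither an upper nor a lower limit: missing data and exclusions from the FAS lower power, adjustment may raise it, and the net direction cannot be settled from the documents. The tests themselves remain valid; only the description of the trial's size and power is wrong as written.

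**What to change.** In Sections 1.1 and 3, label the 400 patients and the listed powers as the original design, not reached because of early termination, and state that 137 were randomised.

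Add to Section 3, with the three assumptions named:
- At SD 2.6, primary power is about 35/43/52% at 0.7/0.8/0.9 points, with a 95% CI half-width of about 0.88. Key secondary power is about 18/28/39% at correlation 0.
- As a sensitivity case at SD 2.0, identified as the 4-week PHN value that the SAP did not adopt, primary power is about 53/64/74%, with a half-width of about 0.68.

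Do not describe these as upper-end figures. Optionally, name the 95% CI of the treatment difference in Section 5.5.1.1, which now mentions CIs only for LS means.

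The cost is a few lines of SAP text. No test, alpha level, estimand or dataset changes; the only downside is a less favourable stated power.
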